11.7 Where and how data or specimens will be stored?

Response: Please see 11.4. Password-protected files are located at Dent Neurologic Institute, and study data are separate from personally identifiable information.

11.8 How long the data or specimens will be stored?

Response: Data will be stored for the duration of the study. Then, any documents or files that acted as personal identifiers for the study will be destroyed at the earliest opportunity. All documents will be placed in one of the HIPAA/Confidential Document bins which are located throughout the Dent Neurologic Institute. These secure bins are then emptied and the documents are destroyed by Cintas. Cintas is certified by the National Association for Information Destruction and also compliant with HIPAA and PCI standards.

11.9 Who will have access to the data or specimens?

Response: Only the PI, Co-Investigator, Statistician, or Research Assistant at Dent Neurologic Institute will have access to the data and participant information.

11.10Who is responsible for receipt or transmission of the data or specimens?

Response: [name] PhD

11.11How data and specimens will be transported?

Response: Data are stored in password-protected files, and will be transferred electronically to the statistician if needed.

12.0 Provisions to Monitor the Data and Ensure the Safety of Subjects

12.1 Describe the plan to periodically evaluate the data collected regarding both harms and benefits to determine whether subjects remain safe.

Response: Please also see section 12.7 pertaining to this question.

Adverse events (AE) will be reported to, evaluated and monitored by the PI, [name]. Any severe adverse event (SAE) will be reported to both the PI and the HSIRB within 24 hours of the research personnel becoming aware of the event. The PI will also evaluate and monitor any severe adverse event. In the event that 20% of the participants should experience an SAE the study will be terminated. In addition to terminating the study due to the previously specified criteria, at any point if the PI should decide to

terminate the study for other reasons, such as no clear evidence of benefit from the study or arising safety concerns, all participants will receive a phone call informing them of the new findings and they will be asked to come in for an early termination visit. Their safety will be assessed, the remaining drug will be collected, and new AEs or SAEs will be recorded. Each participant will also be informed that they will be reimbursed for travel for each visit that they had completed thus far. Reports of adverse events will be continually monitored by co-investigators in order to monitor subject response, ensure subject safety, and determine the necessity for an early termination.

After signing the informed consent, each participant will be assigned a participant number that will be used as coded identification for the entire study. The study's research personnel will compile and analyze incoming data, which will be reviewed on a bi-weekly basis to minimize the risks pertaining to the study. [name] will be responsible for data and safety oversight for the study. Data will be entered by the research personnel and verified at 100%. Data will be password protected, participant identity will be coded and access to identifying information will be limited to ensure confidentiality.

12.2 Describe what data are reviewed, including safety data, untoward events, and efficacy data.

Response: Please see 12.1. Also, the ratio of side effects vs. improvements in symptoms will be specifically evaluated.

12.3 Describe how the safety information will be collected (e.g., with case report forms, at study visits, by telephone calls with participants).

Response: Safety information is collected at every visit; participants are asked about adverse events and complete questionnaires providing feedback on symptoms every visit throughout the duration of the study. Additionally, participants are encouraged to contact study personnel with any concerns, and are required to agree to report any degree of adverse health or psychological complaints regardless of whether or not they believe it is related to the study for the duration of the study including up to 28 days after their participation has concluded.

12.4 Describe the frequency of data collection, including when safety data collection starts.

Response: Data are collected at every visit; every 2 weeks for the first 10 weeks, then every 4 weeks from weeks 10 through 22, then two more visits separated by 1 week each. As previously stated, safety data are collected at every visit.

12.5 Describe who will review the data.

Response: Only the PI, Co-Investigator, Statistician, or Research Assistant at Dent Neurologic Institute will have access to the data and participant information. 12.6 Describe the frequency or periodicity of review of cumulative data.Response: Data will be reviewed bi-weekly.

12.7 Describe the statistical tests for analyzing the safety data to determine whether harm is occurring.

Response: I called IRB on 3/20/2015 to inquire about this and received verbal confirmation that the following procedures pertain to our study:

This is a small (n=12), single location pilot study on the use of Lamotrigine to treat Meniere's disease. The study employs procedures that do not provide sufficient information to conduct statistical testing for potential harm. The main reason for this is because the way in which harm is determined is through probing participants about any side effects, adverse events, or complains at every study visit, as well as providing them with a means of contacting us M-F 8am-4:30pm if they experience any side effects between study visits. Additionally, the consent form outlines specific side effects to watch for that can be associated with the drug, including the course of medical action they should take if they develop the most common allergic reaction (rash). Finally, participants are explicitly asked at the time of consent whether or not they agree to report all adverse effects to the PI or research staff throughout the duration of the study, regardless of whether they believe it is related to the drug or not. All participants must agree to this in order to be in the study. While we have not encountered any adverse events or side effects, if we did, the PI would be informed and we would complete an adverse event report and submit to IRB immediately.

12.8 Describe any conditions that trigger an immediate suspension of the research.

Response: The research will be immediately suspended if the study drug is found to be unsafe due to a drug recall or similar event, or if the safety, security, or functionality of the facilities at which the study takes place become compromised in any way.

13.0 Withdrawal of Subjects

13.1 Describe anticipated circumstances under which subjects will be withdrawn from the research without their consent.

Response: Participants may be withdrawn early without their consent if they develop a rash at any point during the study and [name] decides that it is caused by the treatment, if they develop a serious adverse event other than rash that requires discontinuing involvement in the study, if at any visit they are found to not be following dosing instructions.

13.2 Describe any procedures for orderly termination.

Response: For rash, participants are asked to immediately stop the medication, take an antihistamine, like Benadryl, return for an early termination visit and will be removed early from the study. If a different adverse event is experienced other than a rash, the participant will be asked to return for a visit (for which they are paid as per study compensation guidelines) and begin a two-week decrease of the current study drug dose. This decrease is the current study drug dose once a day for one week followed by half of the study drug dose once a week for another week. If a participant is found to not be following dosing instructions at any visit, [name] will review the situation and determine whether they need to be removed from the study, and if so, the participant will follow the same taper schedule and early termination visit required for those withdrawing due to adverse events other than rash.

13.3 Describe procedures that will be followed when subjects withdraw from the research, including partial withdrawal from procedures with continued data collection.

Response: Participants are informed in the consent form that if they choose to withdraw from the study, there will be no further information collected from them or about them. There isn't an instance of "partial withdrawal" in this study.

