At Visit 2, after the four week lead-in, inclusion/exclusion criteria will be re-evaluated. This includes a review of any concomitant medications. Participants will be asked to hand in their Ménière's survey if they opted for the paper document. The surveys will be reviewed to ensure that abortive measures were only used during the severe attacks, as instructed. The Principal Investigator will assess any possible adverse events and then staff will administer the questionnaire batch. If the participant is eligible for randomization, he/she will be assigned to either a placebo or lamotrigine treatment group. Assignment will be based on a randomization conducted by UBSoPPS Research pharmacists, and the participant will be considered "enrolled" in the study at this point, and from this point on, all medical services, except abortive medication(s) of the patient's choice) are study-related and are not billed to the patient's insurance. Both groups will receive an amber vial of 28 pills with instructions to take one pill twice a day. Those in the lamotrigine group will be taking 25mg BID while those in the placebo group will be taking encapsulated microcrystalline cellulose. A drug dosage log will also be given to participants and they will be asked to write down the number of pills taken. Participants will be advised to notify the Principal Investigator or study staff if they develop rashes or other side effects. If the principal investigator decides that the rash is medication related, the participant will immediately stop the medication, return for an early termination visit and be terminated early from the study. Serious adverse events requiring withdrawal and unrelated to rash will return for an early termination visit and begin a two-week taper. If at any visit a participant is found to be non-compliant with dosing instructions, the Principal Investigator will assess the situation and determine if early termination is required. If the participant is terminated, they will follow the same taper schedule and early termination visit required for those withdrawing due to adverse events other than rash. Staff members will also remind participants to complete the daily survey and how to do so.

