Four weeks later participants return to the clinic for Visit 8, current medications and adverse events will be reviewed by the Principal Investigator. The Principal Investigator will also administer a neurological and physical exam and complete the Clinical Global Impression-Severity and Change assessment. A staff member will collect medication containers, conduct a pill count and collect and review the dosage log and daily Ménière's survey responses. Participants will complete the questionnaire batch, and undergo a comprehensive audiogram with tympanometry. Blood will be drawn, centrifuged and shipped to Kaleida Health's labs to analyze study drug levels, CMP, CBC, and a urine pregnancy test will be conducted for female participants of reproductive age (<50yrs). Additionally, a urine sample will be obtained for 24 hour creatinine clearance analysis as a screening measure for healthy kidney and liver function. At the conclusion of the visit a staff member will be un-blinded by unsealing an envelope that contains treatment code and participant number. Those in the lamotrigine group will be given the option to be terminated from the study, but to continue the study medication at their own cost. Alternatively, they can continue in the study and begin to taper off the study drug. Those who decide to continue the study medication will be noted, but no further study participation is required. Participants continuing lamotrigine will be free to follow up on their treatment through the Dizziness and Balance Clinic or through a physician of their choice. Participants who decide to discontinue the study drug will begin a two-week taper consisting of one week at their current dosage QD and then one week of half the current dosage QD, and be paid for these 2 remaining study visits 9 and 10. Those assigned to the placebo group will be terminated from the study and are informed that they are allowed to seek treatment for their Ménière's disease at the Dizziness and Balance Clinic or elsewhere.

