Those assigned to the lamotrigine treatment will take encapsulated lamotrigine daily for the duration of 20 weeks, consisting of a six-week titration, 12-week study period, and two-week taper. Possible doses for patients are 25mg BID, 50mg BID, 100 mg BID and 150mg BID during titration; 150mg BID or 100mg BID for the 12-week study period; 150mg QD or 100mg QD for Week 1 of the taper; and 75mg QD, or 50mg QD for Week 2 of the taper. Each increase in dose will be maintained for two weeks before deciding to further increase or decrease based on tolerability. Patients who discontinue at any point of the study will have a two-week taper consisting of the current dose QD for one week followed by half the dose QD for another week.

9.5 Describe the source records that will be used to collect data about subjects. (Attach all surveys, scripts, and data collection forms.)

Response:

- □ Ménière's Disease Patients-Oriented Severity Index (MDPOSI)
- □ Tinnitus Handicap Inventory (THI) questionnaire
- □ Clinical Global Impression-Severity & Change
- Dizziness Handicap Inventory (DHI) questionnaire
- □ AAO-HNS Ménière's disease self-assessment
- □ Patient Health Questionnaire-9 (PHQ-9)
- □ Generalized Anxiety Disorder 7-item scale (GAD-7)
- \Box Dosing Log
- □ Meniere's daily survey

9.6 What data will be collected including long-term follow-up.

Response:

Please see 9.5, plus:

 $\hfill\square$ Results of physical and neurological exams

- □ Audiogram
- \Box Drug dosing
- \Box CBC, CMP blood tests
- □ Lamotrigine blood levels (received from lab only after unblinding occurs)
- □ Urine pregnancy test results and creatinine levels
- \Box Drug adherence information
- □ Medications list
- □ Medical history
- 9.7 For HUD uses provide a description of the device, a summary of how you propose to use the device, including a description of any screening procedures, the HUD procedure, and any patient followup visits, tests or procedures.

Response: N/A

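### Section 13.2 sets week 2 of the early-termination taper at one half dose for the whole week, where sections 9.4 and 30.1 set it at one half dose a day

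*Combined protocol and SAP*

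**What the plan says.** The taper after stopping study drug is described in four places in the combined protocol and SAP.

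- **Section 13.2 (orderly termination)** covers adverse events other than rash, and applies the same schedule to participants removed for not following dosing instructions. Week 1 reads "This decrease is the current study drug dose once a day for one week". Week 2 reads "followed by half of the study drug dose once a week for another week".
- **Sections 9.4 and 30.1 (drug sections, same sentence in both)** state: "Patients who discontinue at any point of the study will have a two-week taper". The schedule is "the current dose QD for one week followed by half the dose QD for another week". Both sections also list the taper doses: 150 or 100 mg QD in week 1, and 75 or 50 mg QD in week 2.
- **Section 9.2, Visit 8** gives completers who stop lamotrigine "one week at their current dosage QD and then one week of half the current dosage QD".

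For rash, section 13.2 says "For rash, participants are asked to immediately stop the medication". Section 9.2 says that, when the rash is judged medication related, "the participant will immediately stop the medication, return for an early termination visit and be terminated early from the study". Section 14.1 also requires immediate discontinuation for a study-related rash.

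**The concern.** Section 13.2 and sections 9.4 and 30.1 prescribe different week 2 dosing for the same participants. The first allows one half dose in the week; the others allow one each day. Section 13.2 is where staff would naturally look when a participant leaves early. Someone following it to the letter would in effect end daily dosing after week 1, which defeats the purpose of a two-week step-down.

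What is at stake is a patient dosing instruction, not the trial's inference. The documents give no estimate of the harm from a faster taper, so the size of the problem can be stated only in doses and milligrams.

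**Working it through.** **Inputs**

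- Unit dose before stopping, d: 25, 50, 100 or 150 mg, taken BID (section 9.4). Early leavers can be at any of these levels, because they may stop during titration.
- Week 1: d once daily. All sections agree.
- Week 2: d/2 once daily (9.4, 30.1, and 9.2 for completers), or d/2 once in the week (13.2).

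**Reproducing the plan's own figures.** From 150 mg BID, week 1 is 150 mg QD and week 2 is 150/2 = 75 mg QD. From 100 mg BID, week 1 is 100 mg QD and week 2 is 100/2 = 50 mg QD. These match the doses listed in 9.4 and 30.1.

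**Formulas.** Week 2 total, daily rule = 7 × d/2. Week 2 total, weekly rule = d/2. The ratio is 7 at every dose.

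| Dose before stopping | Week 2, daily rule | Week 2, weekly rule | Difference | Two-week total, daily rule | Two-week total, weekly rule |
|---|---|---|---|---|---|
| 150 mg BID | 7 × 75 = 525 mg | 75 mg | 450 mg | 1050 + 525 = 1575 mg | 1050 + 75 = 1125 mg |
| 100 mg BID | 7 × 50 = 350 mg | 50 mg | 300 mg | 700 + 350 = 1050 mg | 700 + 50 = 750 mg |
| 50 mg BID | 7 × 25 = 175 mg | 25 mg | 150 mg | 350 + 175 = 525 mg | 350 + 25 = 375 mg |
| 25 mg BID | 7 × 12.5 = 87.5 mg | 12.5 mg | 75 mg | 175 + 87.5 = 262.5 mg | 175 + 12.5 = 187.5 mg |

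**Which rule is intended.** Three points favour daily dosing. The week 1 half of the 13.2 sentence is itself daily. The drug sections give daily week 2 dosing both as a rule and as listed doses. Completers receive the daily rule as well. Nothing else in the protocol supports a single dose in week 2.

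**Reach.** Section 23.2 anticipates about 2 to 5 dropouts, and the 6/4/2015 update in section 11.2 reports 2. Not every dropout would taper, and some are on placebo. The documents do not say how many participants would use the 13.2 schedule, and section 12.7 reports no adverse events or side effects up to the time it was written.

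**The case against.** The strongest reply is that the text corrects itself: a careful reader who compares the sections will see one slip against several consistent statements and will dose daily. That is fair, and it is why the severity is low. It does not remove the need to correct the sentence, because a dosing instruction should not depend on the reader checking other sections.

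Two stronger readings are tempting, and the documents do not support them.

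- **A separate, faster regimen for early leavers.** A reader might infer that 13.2 deliberately differs from the completers' taper in 9.2. Sections 9.4 and 30.1 rule this out, because they expressly cover discontinuation at any point and still give the daily schedule.
- **A second contradiction, on rash.** The general sentence in 9.4 and 30.1 has no exception for rash, so a reader might infer that a participant with a drug rash is to be tapered, with up to 1575 mg of further exposure. But the immediate stop is stated in 9.2, 13.2 and 14.1, and 13.2 keeps its adverse-event taper for events other than rash. Section 9.2 does the same: "Serious adverse events requiring withdrawal and unrelated to rash will return for an early termination visit and begin a two-week taper". A general sentence read together with specific rules is ordinary drafting, and no extra exposure is expected. A cross-reference would help, but this is not an error in its own right. The risk of serious rash named in 14.1 also has no bearing on the week 2 slip, which concerns non-rash withdrawals and non-compliance only.

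**Conclusion.** The point holds as an internal inconsistency in a dosing rule. Taken literally, section 13.2 gives one seventh of the week 2 drug that sections 9.4 and 30.1 give to the same participants, a shortfall of 75 to 450 mg depending on the dose at stopping. The milligram figures assume that the current dose means the unit dose taken at each administration, which the listed taper doses confirm, and that 13.2 would be followed to the letter.

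Severity is low. The intended schedule is recoverable and the number of participants affected is small, though the documents do not let it be fixed. The primary endpoint, the power calculation and the planned analyses are all unchanged.

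**What to change.** In section 13.2, change the week 2 frequency from once a week to *once a day*, so that the sentence gives half of the study drug dose *once a day for another week*.

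Optionally, in the discontinuation sentence of sections 9.4 and 30.1, add *except for medication-related rash, when the drug is stopped immediately without taper*. This only repeats the rule already in 9.2, 13.2 and 14.1.

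The cost is one word in 13.2, plus one clause in two places if the clarification is adopted, all in a single amendment. No procedures, visits or participants are added.

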Participants who are diagnosed with Ménière's disease, as determined by clinical history, ENT confirmation and an audiogram, will qualify if they also have had two or more Ménière's vertigo attacks in a four-week span for two consecutive four-week periods (the qualification period). Those who meet these criteria will then need two or more Ménière's vertigo attacks during a four-week lead-in period to further establish a baseline and verify randomization eligibility. Participants are allowed from the beginning of the lead-in to take their choice of a symptomatic abortive medication according to its package instructions for Ménière's vertigo attacks that last longer than 30 minutes with nausea and/or vomiting. Symptomatic abortive medications include, but are not limited to, meclizine (Antivert), Valium, diazepam, or Zofran. The abortive medication can be used throughout the study regardless of treatment assignment and its use will be recorded. Twelve eligible participants, with a minimum total of six attacks during the qualification and lead-in periods, will be randomly assigned to either a placebo or lamotrigine treatment group. Randomization will be conducted by UBSoPPS Research Pharmacy. The study drug and matching placebo will be titrated from 25mg twice a day (BID) up to 150mg BID over a six week period. During titration, clinic visits are scheduled every two weeks to assess any adverse events, symptoms, quality of life, and compliance. Those who cannot tolerate the 150mg BID dose may return to a 100mg BID dose during an unplanned visit. However, if a participant is unable to tolerate the 100mg BID dose they will be withdrawn from the study. Participants will maintain the 150mg BID or 100mg BID dose for a 12-week period with clinic visits every four weeks to assess their progress. Between all study visits, participants are asked to complete a daily survey describing their symptoms. This survey is hosted by polleverywhere.com and can be completed through text message, an online website, or with a paper document- whatever method is preferred by the participant. At the conclusion of the 12-week study period, a study staff will be un-blinded

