11.0 Data Management

11.1 Describe the data analysis plan, including any statistical procedures.

Response: The primary response will be the number of vertigo attacks as measured at baseline and at the end of the study period. The secondary responses will include the percentage of vertigo free patients, audiograms, symptom severity scales and quality of life scales (listed in the Approach section). The analysis set will include all subjects who are randomized and receive at least one dose of the study medication or the placebo. Integer or continuous variables will be presented by their mean and median and their SD and IQR. Categorical variables will be summarized using counts and percentages. Demographic and baseline characteristics of the enrolled subjects will be summarized through descriptive statistics for continuous variables and through frequencies for categorical variables. Demographic and baseline characteristics of the intervention and placebo groups will be compared to assess for comparability. Continuous variables will be compared using Wilcoxon rank-sum test and categorical variables will be compared through Fisher's exact test. We will test for reduction in the Ménière's vertigo attacks from baseline through Wilcoxon's sign rank test and will compare the reduction between the two treatment groups using Wilcoxon rank-sum test. The tests will be two-tailed and the significance level will be set to 0.05. Additionally, we will perform statistical modeling of the number of vertigo attacks longitudinally through generalized linear mixed effects model using Poisson or Negative Binomial distribution as appropriate. Data analysis will be conducted using SAS (SAS Institute Inc., Cary, NC, USA) and R (http://www.r-project.org/). All data analyses will be performed by [name] of the SUNY UB Statistical Consultant Laboratory.

11.2 Provide a power analysis.

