Response: Participants will be reimbursed \$35 per visit, up to \$315 total (6-8 visits for placebo & Lamotrigine groups, respectively, plus 1 extra visit if needed for a maximum of 9 visits). Payment will be made by check and mailed to the participant's address as written on their signed Declaration of Participation form. Should the participant choose to drop out of the study or the study is terminated, a check will be mailed after

completion of the early termination visit or after completion of the most recent visit prior to dropping out.

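### Section 13.3 stops all data collection when a participant chooses to withdraw, while 11.1 keeps that participant in an analysis that needs an end-of-study attack count

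*Combined protocol and SAP*

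**What the plan says.** Section 13.3 covers participants who choose to leave. It reports that they are told in the consent form that, "if they choose to withdraw from the study, there will be no further information collected from them or about them". It also states that the study has no partial withdrawal. Removal by the investigator (drug-related rash, another serious adverse event, not following dosing instructions) is handled separately in 13.1 and 13.2.

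Section 11.1 defines the analysis: "The analysis set will include all subjects who are randomized and receive at least one dose of the study medication or the placebo". On the outcome it says: "The primary response will be the number of vertigo attacks as measured at baseline and at the end of the study period". The reduction from baseline is compared between groups by a two-sided Wilcoxon rank-sum test at 0.05. A longitudinal mixed model for the counts is planned in addition. No rule is given for a missing end-of-study count.

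Three other places touch on people who leave:
- Section 12.3 has participants agree to report complaints during the study, "including up to 28 days after their participation has concluded".
- Section 9.4 (repeated in 30.1) says: "Patients who discontinue at any point of the study will have a two-week taper".
- Section 22.5 pays a person who drops out after "completion of the early termination visit or after completion of the most recent visit prior to dropping out", so it does not make the early termination visit certain.

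The 11.2 update records 2 dropouts and 8 completers and raises the total to 16. Section 23.2 expects 2-5 dropouts.

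**The concern.** The two rules do not fit together. Under 11.1 a dosed participant who chooses to leave belongs in the primary comparison. Under 13.3 nothing may be collected after that person leaves, so the value the comparison needs will not exist. If the plan is followed exactly, the rank-sum test will in practice be run on completers only.

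That matters if leaving is related to how the person is doing. Someone who leaves because attacks continue, or because attacks have stopped, has an end count unlike those who stay. The mixed model can use counts recorded before leaving, but only by assuming that the unseen later counts follow the same pattern. At 12-16 participants, one or two such values can decide whether the result is significant.

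A lesser issue is that 12.3 expects reports after participation ends, while 13.3 says nothing more is collected. The plan does not say which applies to a voluntary leaver.

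**Working it through.** **Reproducing the plan's enrolment figure.** The inputs are 12 completers needed (23.2) and the stated dropout rate of 25% (11.2 update). 12 / (1 − 0.25) = 16. The update's own wording, 12 × 1.25 = 15 brought to equal groups, also gives 16. At that rate 16 × 0.75 = 12 completers, so the increase protects the number of completers. It does not supply values for those who leave.

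**How many end counts could be missing.** The documents do not split dropouts by reason, so the number of voluntary leavers is an assumption. Taking 1, 2 or 5 of 16:
- 1 leaver: 15/16 = 94% have an end count.
- 2 leavers: 14/16 = 88%.
- 5 leavers: 11/16 = 69%.

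**How far missing values could move the primary test.** Assumptions: 8 v 8 allocation, no ties, exact two-sided rank-sum test. U is the number of lamotrigine-placebo pairs that go against lamotrigine, and p = 2 × (arrangements with U no larger than observed) / C(n1+n2, n1). A missing value is placed at the most or least favourable rank. This holds for reductions from baseline because only ranks are used.

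One missing per arm:
1. The largest significant U for 7 v 7 is 8: p = 2 × 65/3432 = 0.0379.
2. Worst case: the lamotrigine leaver loses to all 8 placebo participants (+8), and the placebo leaver beats the 7 observed on lamotrigine (+7). U = 8 + 8 + 7 = 23 in 8 v 8: p = 2 × 2460/12870 = 0.382.
3. Best case: nothing is added, so U = 8 in 8 v 8: p = 2 × 67/12870 = 0.0104.
4. Even complete separation of the 14 observed (U = 0) becomes U = 15 in the worst case: p = 2 × 534/12870 = 0.083.

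One missing in total:
1. The largest significant U for 7 v 8 is 10: p = 2 × 129/6435 = 0.0401.
2. Worst case: U = 10 + 8 = 18, p = 2 × 1033/12870 = 0.1605.
3. Best case: U = 10, p = 2 × 133/12870 = 0.0207.

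**What can still be recovered.** With 8 completed and 2 already gone, at most 16 − 8 − 2 = 6 participants can be affected by an amendment, and at most 14 end counts can exist.

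**The case against.** Ending collection when someone withdraws is a permissible choice, and participants must be free to refuse all contact. An analysis set can be honoured with data gathered before withdrawal, and the mixed model would use them. The consent form is not in the copy reviewed, so it may reconcile these texts. Following people after they stop drug brings off-treatment counts into a proof-of-concept comparison. All of this is fair. What stands is that the rank-sum test cannot use a participant without an end value, and nothing in 11.1 says what to do then.

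Four stronger readings are tempting, and the documents do not support them:
- **Power falls from that of 16 end counts.** The plan never relied on 16; it needs 12 completers. In a simulation of end counts at the planning means (5 v 13), 6 v 6 gives about 49% power with SD 7.24 and 79% with SD 4. Two leavers of 16 leave 60% and 88%, which is above that level. The simulation also tests end counts, not the reduction that 11.1 tests.
- **Section 12.7 narrows the reporting duty.** It describes reporting "throughout the duration of the study, regardless of whether they believe it is related to the drug or not", without mentioning the 28 days. But 12.3 counts the 28 days within the duration of the study, so 12.7 is shorter wording, not a lesser duty.
- **The 9.4 taper contradicts 13.3.** Section 9.4 is a dosing rule and does not itself require data from early leavers.
- **Serious harm could be missed, or the 20% stopping rule in 12.1 defeated.** The plan gives no serious adverse event rate, self-report under 12.3 remains, and a rash that the investigator judges drug-related falls under 13.1 and 13.2, not 13.3.

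**Conclusion.** The point holds for voluntary leavers and concerns the primary data. Following 13.3 exactly removes the value that 11.1 needs, and the increase to 16 addresses numbers, not bias. With one missing count per arm, a just-significant result is bounded by p = 0.010 and p = 0.38; with one missing in all, by 0.021 and 0.16.

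These bounds rest on 8 v 8 allocation, no ties and extreme placement of the missing values. They show what the data could not rule out, not what is likely. The number of voluntary leavers is unknown. The safety side is a matter of clarifying 12.3, and the loss there is small. The change should be made because it is cheap and brings the data collected into line with the stated analysis set.

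**What to change.** 1. In 13.3 and the consent form, separate stopping study drug from leaving the study. Invite those who stop drug to attend the early termination visit and to continue the daily survey to the planned end of the 12-week study period. Close data collection only for those who refuse further contact.
2. In 12.3, state that the 28-day reporting covers people who leave early.
3. In 11.1, include counts collected after stopping drug in the primary comparison. Add a sensitivity analysis that places any end counts still missing at the best and worst ranks.

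The cost is one amendment, with the re-consent of current participants that section 28 already provides for, and a few contacts per leaver. No new instrument is needed, since 9.1 says the survey "can be completed through text message, an online website, or with a paper document". Off-drug counts may dilute the treatment effect, which is the price of analysing everyone dosed. Some leavers will still refuse contact, which is why step 3 is needed, and the two participants who had already left cannot be recovered.
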